2. ANALYSIS SETS

2.1 Definition of analysis sets

All subjects analysis set:

This analysis set comprises all enrolled subjects who signed the informed consent form, and will be used for reporting of disposition including screen failures.

Randomised subjects analysis set:

This analysis set comprises all subjects randomised to study treatment, irrespective of whether IP was subsequently taken, and will also be used for reporting of disposition.

2.1.1 Efficacy analysis set

Full analysis set (FAS)

This analysis set comprises all subjects randomised to study treatment who received at least one dose of IP, irrespective of their protocol adherence and continued participation in the study.

Evaluable analysis set

This analysis set comprises all subjects randomised to study treatment who completed at least 20 weeks of study treatment and had an EOT visit date not greater than 8 weeks after date of last dose of IP.

Efficacy analyses will be performed using all subjects in the evaluable analysis set unless otherwise stated, with subjects classified by their randomized treatment according to the intention-to-treat (ITT) principle. Subjects will be analysed according to their randomised treatment (including in the case of any discrepancies between randomised and actual treatment).

The evaluable analysis set and FAS specifies which subjects are included in efficacy analyses. Details of which data are included in efficacy analyses for these subjects are given in the respective sections, notably in Section 3.1.5 and Section 4.2.

Certain types of exploratory efficacy data are planned to be captured in a subset of participating subjects who have given an additional consent to participate in such a sub-study. Where this is the case, the analysis will use the subset of subjects in the evaluable analysis set for which any data of the relevant type are available. No formal sub-study analysis sets will be explicitly defined for this purpose.

2.1.2 Safety analysis set

Safety analysis set

This analysis set comprises all subjects who received at least one dose of IP.

Safety analyses will be performed using all subjects in the safety analysis set. Subjects will be analysed according to their actual treatment in the case of any discrepancies between randomised and actual treatment. Specifically, a subject who has on one or more occasions actually received active (tezepelumab) treatment will be assigned to the tezepelumab group, regardless of the randomised treatment assignment. A subject who has on no occasion actually received any active (tezepelumab) treatment will be assigned to the placebo group, regardless of the randomised treatment assignment.

Safety data will also be listed separately and discussed in the CSR for any subject who received a treatment at one or more visits which was not the randomised treatment.

Summaries of ADA will also be based on the safety analysis set, using the same approach to handle treatment dispensing errors.

2.1.3 Other analysis set

PK analysis set

This analysis set comprises all subjects in the FAS who received active (tezepelumab) treatment and had at least one detectable tezepelumab serum concentration from a PK blood sample collected post first dose which are assumed not to be affected by factors such as protocol deviations.

Summaries of PK will be based on the PK analysis set.

2.1.4 Handling of other issues which may impact analysis sets

If it is found that any subject has been randomised on more than one occasion (contrary to the protocol) under different subject numbers, either at the same site or at different sites, then the first subject occurrence will be included in the relevant analysis sets defined above, and only

data associated with that first subject occurrence used in all analysis. Data associated with the second (and any subsequent) occurrences of the same subject will be listed and discussed in the CSR. All data associated with duplicate randomisations will be reviewed, and decisions regarding the analysis and reporting of these data will be documented, prior to unblinding.

The above analysis set definitions assume the integrity of data captured from all participating sites in the trial. If it is deemed necessary to exclude subjects from analysis sets due to suspected fraud/other serious non-compliance at a particular site, or to perform sensitivity analyses with subjects from such a site removed for the same reason, this will be documented in this SAP (amended if necessary) where this is possible prior to database lock (DBL). Otherwise, it will be fully described in the CSR. The SAP will not be updated for this after DBL.

2.2 Violations and deviations

Only important PDs will be listed and tabulated in the CSR, and only for randomised subjects (i.e. not screening failures). These are defined as PDs which may significantly affect the completeness, accuracy and/or reliability of the study data, or which may significantly affect a subject's rights, safety or well-being. They may include (but not be limited to):

- Subjects who were randomised even though they did not meet all inclusion criteria or at least one exclusion criteria applied
- Subjects who met discontinuation criteria for study treatment but were not withdrawn from study treatment
- Subjects who developed withdrawal criteria during the study but were not withdrawn
- Subjects who received the wrong treatment or an incorrect dose
- Subjects who received a restricted or prohibited concomitant treatment.

All important PDs will be identified and documented by the study team prior to unblinding of the trial. As far as possible, the occurrence of important PDs will be monitored (blinded) during the trial, with the emphasis on their future prevention.

Except for the PK analysis set, PDs including important PDs, will not be used to exclude any subject from any analysis set, nor to exclude any data from subjects included in an analysis set.

The study non-compliance handling plan outlines the management of important PDs, and includes the proposed categories of important PDs in this trial. Any PDs which are not defined as important (excluding COVID-19 related PDs) will not be reported or discussed in the CSR.

The COVID-19 related violation and deviations are described in Appendix 8.3.

3. PRIMARY AND SECONDARY VARIABLES

3.1 General definitions

3.1.1 Definition of baseline

In general, the last non-missing measurement on or prior to the date of randomisation will serve as the baseline measurement for efficacy variables. If there is no value on or prior to the date of randomisation, then the baseline value will not be imputed, and will be set to missing.

In general, the last non-missing measurement prior to the first dose of study treatment will serve as the baseline measurement for safety, pharmacokinetic and immunogenicity variables. If there is no value prior to first dose of study treatment, then the baseline value will not be imputed, and will be set to missing.

Where unscheduled/repeat assessments are relevant and exist for any subject at a particular visit specified below, they will also be considered in the baseline definitions, provided they remain on or prior to the date of randomisation (efficacy) or prior to the date of first dose of study treatment (safety).

For daily assessments which are made in both morning and evening, the whole day is defined by the assessments in the evening and the following morning. The daily assessment will be considered missing if either evening or following morning is missing. However, some analyses may consider morning and evening separately.

For safety variables (vital signs, weight/body mass index (BMI), haematology, clinical chemistry, urinalysis, 12- or 15-lead ECG), baseline will be defined as the latest non-missing assessment prior to first dose. If no time is recorded for an assessment, and the assessment takes place at Visit 3b, this will be assumed to be a pre-dose assessment.

3.1.2 Absolute change from baseline

Absolute change from baseline is defined as *(post-baseline value – baseline value)*.

If either the post-baseline value or the baseline value is missing, then the absolute change from baseline will also be missing.

Unless otherwise specified, “change from baseline” is assumed to be the absolute change from baseline.

3.1.3 Percent change from baseline

Percent change from baseline is defined as $[(\text{post-baseline value} - \text{baseline value})/\text{baseline value}] \times 100\%$.

Unless otherwise specified, if either the post-baseline value or the baseline value is missing, then the percent change from baseline will also be missing.

For percent change from baseline, if the baseline value for a subject is zero, the baseline value will be replaced by half the smallest observed value among subjects with non-zero values, before calculating the percent change from baseline. If both baseline and post-baseline values for a subject are zero, the value for the percent change is defined to be 0.

3.1.4 Reversibility

Percentage reversibility is defined as follows, for pre-BD and post-BD measurements taken on the same date:

$$\%Reversibility = [(post-BD FEV_1 - pre-BD FEV_1)/pre-BD FEV_1] \times 100\%$$

The FEV₁ post-BD measurement in the reversibility derivation is the measurement after up to 4 SABA inhalations.

3.1.5 Study periods

The following study periods are defined for analysis purposes:

- Screening/run-in period: starting on the date of the first study procedure and ending one day prior to randomisation (for randomised subjects) or on the date of the last study procedure (for screening failures). If any subject is re-screened, the latest available screening will be used for this purpose.
- Planned treatment period: starting on the date of randomisation (efficacy) / date of first dose of IP (safety) and ending on the date of the EOT visit or earlier study withdrawal date (for subjects not followed up until the EOT visit)
- On-treatment period: starting on the date of randomisation (efficacy) / date of first dose of IP (safety) and ending on minimum (date of last dose of IP + 35 days, date of death, date of study withdrawal).
- Post-treatment period/Follow-up period: starting one day after the end date of on-treatment period and ending on the study completion or withdrawal date.
- On-study (on-treatment and post-treatment) period: starting on the date of randomisation (efficacy) / date of first dose of IP (safety) and ending on the study completion or withdrawal date.

Efficacy analyses will use data collected during the planned treatment period, except for lung function and some biomarker data that will use data collected at the protocol specified time points for the on-study period.

Safety analyses will be presented for data collected during the on-treatment period and on-study period.

3.1.6 Visit windows

All summaries and analyses, both efficacy and safety, which are presented by time point (e.g. “Week 28”) will use a visit window to classify the data record, which is derived from the assessment date relative to the reference start date. This approach allows appropriate classification of visits which may have occurred significantly earlier or later than the protocol assessment schedule, as well as the use of data captured at visits which have no fixed timing (notably the IPD visit), and the handling of data captured at visits for which the database label is incorrect and unresolvable.

Nominal database visit numbers will not be used in any summary or analysis by visit.

For efficacy variables, the reference start date is the date of randomisation, and relative day is therefore defined as $(date\ of\ assessment - date\ of\ randomisation) + 1$.

For safety variables, the reference start date is the date of first dose of IP, and relative day is therefore defined as $(date\ of\ assessment - date\ of\ first\ dose\ of\ IP) + 1$.

Any data collected at unscheduled or repeat visits will be listed, and will be included in baseline definitions (see Section 3.1.1), and in any definitions of maximum value, minimum value or last value within the relevant study period.

Data collected at unscheduled or repeat visits will also be included in visit windows, and therefore may be included in summaries or analyses by visit, or used in any sensitivity analyses which involve imputation of data from subjects with non-missing values to subjects with missing values. In the case of a missing value at a scheduled visit, which is then followed by a non-missing value at an unscheduled or repeat assessment within the same visit window, the non-missing value at the unscheduled/repeat assessment will replace the missing value at the scheduled visit.

If a subject has more than one non-missing value within the same visit window, the following rules will apply:

- The non-missing value closest to the target day will be selected for analysis at that visit
- If two non-missing values are the same distance from the target day, the earlier of the two values will be selected for analysis at that visit
- If two non-missing values are recorded on the same day and have a different assessment time associated with both of them, the value with the earliest assessment time will be selected for analysis at that visit.
- If two non-missing values are recorded on the same day and have no assessment time associated with at least one of them, or the same assessment time associated with both of them, the average of the two values will be selected for analysis at that visit.
- If there are multiple ADA samples in the same visit window with both positive and negative results, the sample with a positive result and the highest titre value should be selected.

If a subject has no value within a particular visit window, then the subject will have a missing value at that visit in summaries and analyses.

The same visit window definitions below will be used regardless of whether the planned treatment, on-treatment, or on-study period is used for analysis (see Section 3.1.5). In practice, each data record in the planned treatment period will be identified, and then additional flags are created according to whether it is in the on-treatment or post-treatment, or on-study periods. These flags will be used to select all eligible records for subsequent visit windowing, according to whether the derived visits are to be used in a planned treatment, on-treatment, or on-study period analysis. It should be noted that, if treatment was discontinued within a particular visit

window, the rules above for handling multiple values within the same visit window could select a different record according to whether a planned treatment period analysis or an on-treatment period analysis is needed.

In planned treatment period analysis, any off-treatment assessments measured at a follow-up visit (scheduled 16 weeks after last IP administration) which occurred earlier than scheduled follow-up visits week 32, week 36, week 40, or later due to COVID-19 pandemic will be considered in earlier planned treatment period visit windows, where applicable.

The following table summarises the visit windows to be used. “Visit window 1” corresponds to the full (mostly 4-weekly) protocol scheduling and will be used for all variables by default, including those variables which are not captured according to the full protocol schedule, and for which only certain weeks displayed in “Visit window 1” therefore apply. An assessment will be made during blinded review of the extent to which values for variables which do not follow the complete protocol schedule are falling outside the windows for the relevant weeks using “Visit window 1”. Following blinded review, a decision may be made to apply one of the alternative visit window rules displayed below to any such variables.

Table 1 Visit windows

Time point	Target day	Visit window 1	Visit window 2 (if needed)	Visit window 3 (if needed)	Visit window 4 (if needed)
Baseline (Week 0)	1	See Section 3.1.1 for baseline definitions			
Week 2	15				
Week 4	29	2-42			
Week 8	57	43-70			
Week 12	85	71-98	2-140		2-140
Week 16	113	99-126			
Week 20	141	127-154			
Week 24	169	155-182			
Week 28/EOT*	197/EOT*	183-210/EOT*	141-210/EOT*	2-210/EOT*	141-210/EOT*
Follow-up Week 32*	225				
Follow-up Week 36*	253				
Follow-up Week 40*	281	211-294	211-294		

* During the COVID-19 pandemic unscheduled visits may occur at week 28, 32, 36, 40, 44 or until 48 so that sites may perform EOT assessments 4 weeks after last dose of IP. After EOT visit, there will be post-treatment follow-up period of 12 weeks. Data from EOT visit will be summarised as “EOT” time point without visit window applied.

Finally, it should be noted that a visit window approach will not be used for data captured on a device daily by the subject, which will be aggregated for analysis at each relevant time point by using a weekly mean or similar approach. For this purpose, the definition of the weekly mean is provided in the relevant endpoint derivation sections of this SAP.

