4.2.9 Pharmacokinetics and immunogenicity

4.2.9.1 Analysis of pharmacokinetics

All analyses of PK variables will be based on the PK analysis set as defined in Section 2.1.3.

Serum tezepelumab concentrations will be summarised at the protocol specified time points for the on-study-period using descriptive statistics (for the tezepelumab group only).

Serum samples for PK are scheduled to be collected at weeks 0, 12, EOT visit (or the premature IP discontinuation visit, where appropriate), and final follow-up at 12 weeks after EOT visit. Data will be assigned to weeks based on the windows defined in [Section 3.1.6](#).

The following criteria will also apply for data to be included in the summary table:

- Only pre-dose samples at week 0.
- Only pre-dose samples at trough time points (week 12) that was also between ≥ 21 and ≤ 35 days post the previous dose.
- Only samples at EOT visit/premature IP discontinuation visit that were taken between ≥ 21 and ≤ 35 days post the last dose.
- Only samples at final follow-up visit that were taken between ≥ 98 and ≤ 126 days post the last dose.

For descriptive statistics of tezepelumab concentrations:

- If, at a given time point, 50% or less of the concentrations are non-quantifiable (NQ), the geometric mean, coefficient of variation (CV), arithmetic mean and SD will be calculated by substituting the lower limit of quantification (LLOQ) divided by 2 for values which are NQ.
- If more than 50%, but not all, of the concentrations are NQ, the geometric mean, CV, arithmetic mean and SD will be reported as not calculable (NC)
- If all the concentrations are NQ, the geometric mean and arithmetic mean will be reported as NQ and the CV and SD as NC
- The median, minimum and maximum will also be reported.

The LLOQ of tezepelumab in serum will be 0.010 $\mu\text{g/mL}$.

The PK data may be merged with those from other clinical studies for a population-based meta-analysis. If performed, results of the meta-analysis will be presented in a separate pharmacometrics report outside of the CSR, and this is not considered further in this SAP.

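### The follow-up window stays at days 211-294 when extra COVID-19 doses are given, so the final follow-up visit of extended subjects falls outside every window in the by-visit summaries

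*SAP*

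**What the plan says.** SAP Section 3.1.6 applies windows to every summary by time point. The clock is fixed at study start: "For safety variables, the reference start date is the date of first dose of IP", and for efficacy variables it is randomisation. Visit labels cannot override the clock, since "Nominal database visit numbers will not be used in any summary or analysis by visit". Unscheduled visits are not set aside: "Data collected at unscheduled or repeat visits will also be included in visit windows". A value outside the windows is lost to the table: "If a subject has no value within a particular visit window, then the subject will have a missing value at that visit".

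Table 1 has one follow-up window, in the row "Follow-up Week 40* 281 211-294 211-294". The Week 32 and Week 36 follow-up rows have none of their own.

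Section 1.2 allows up to six extra 4-weekly doses during the pandemic, and Appendix 8.3 places them at weeks 28 to 48. The Table 1 footnote says "During the COVID-19 pandemic unscheduled visits may occur at week 28, 32, 36, 40, 44 or until 48", puts EOT assessments 4 weeks after the last dose, gives a 12-week follow-up after EOT, and exempts EOT data from windowing. It carries no equivalent statement for follow-up data.

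For serum concentration, Section 4.2.9.1 schedules the final sample 12 weeks after EOT and says "Data will be assigned to weeks based on the windows defined in" Section 3.1.6. It then adds a second condition, beginning "Only samples at final follow-up visit that were taken between", that admits only samples 98 to 126 days after the last dose.

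**The concern.** The November 2020 update moved EOT with the extra doses but left the follow-up window where it was. Follow-up is timed from EOT, and EOT from the last dose, so each extra dose pushes the final visit 28 days later while the window stays fixed. Two things can go wrong in the follow-up row: values that belong there are absent, and values taken while the subject is still being dosed are present.

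Section 1.2 gives the purpose of the follow-up period as assessment of safety parameters and ADAs. The by-visit follow-up rows for laboratory data, vital signs, ADA and serum concentration are where the off-treatment picture would be read. Applied literally, the plan leaves extended subjects' final values out of those rows and limits the washout PK row to subjects without extra doses.

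**Working it through.** **Inputs.** Table 1: target days and the window 211-294. Section 1.2: dosing every 4 weeks, up to six extra doses. Table 1 footnote: EOT = last dose + 4 weeks; follow-up = EOT + 12 weeks. Section 4.2.9.1: PK follow-up samples 98-126 days after last dose. Inferred: the last regular dose is at week 24, because EOT is week 28 and falls 4 weeks after the last dose.

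**Reproducing Table 1.** Target day = 7 × week + 1. Week 24 gives 169, week 28 gives 197, week 40 gives 281, as tabulated. Last dose 169 + 112 days (the 16 weeks stated in Section 3.1.6) = 281, the tabulated follow-up target. So 211-294 is correct for a subject with no extra dose.

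**With k extra doses, at nominal timing.** Last dose = 169 + 28k. EOT = last dose + 28. Final follow-up = EOT + 84. PK-eligible days = last dose + 98 to last dose + 126.

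| k | Last dose | EOT | Final follow-up | Days past 294 | PK-eligible days | Days shared with 211-294 |
|---|---|---|---|---|---|---|
| 0 | 169 | 197 | 281 | inside | 267-295 | 28 |
| 1 | 197 | 225 | 309 | 15 | 295-323 | 0 |
| 2 | 225 | 253 | 337 | 43 | 323-351 | 0 |
| 3 | 253 | 281 | 365 | 71 | 351-379 | 0 |
| 4 | 281 | 309 | 393 | 99 | 379-407 | 0 |
| 5 | 309 | 337 | 421 | 127 | 407-435 | 0 |
| 6 | 337 | 365 | 449 | 155 | 435-463 | 0 |

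For every k of 1 or more, the final visit is in no window and the two PK conditions cannot both be met.

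**Where the extra-dose visits land.** Week 28 (day 197) falls in Week 28/EOT. Weeks 32, 36 and 40 (days 225, 253, 281) fall in 211-294, week 40 exactly on its target day. Weeks 44 and 48 (days 309, 337) fall in no window. A subject with one extra dose is dosed only at day 197, so a dosing visit can be labelled follow-up only with two or more extra doses. The closest-to-target rule would favour a week-40 value, while for ADA Section 3.1.6 selects the positive sample with the highest titre when a window holds both positive and negative results. For PK, the 98-126-day condition keeps any such sample out of the follow-up row.

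**Does another rule rescue this?** Section 3.1.6 allows a switch to another window after blinded review, but Visit window 2 repeats 211-294 and Visit windows 3 and 4 have no follow-up window. The sentence about follow-up visits occurring later because of the pandemic applies to planned-treatment-period analyses and sends records to earlier windows. The laboratory, vital-sign, PK and ADA by-visit summaries use the on-study period (Sections 4.2.8.2, 4.2.8.3, 4.2.9.1, 4.2.9.3).

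**The case against.** A reader might infer that all follow-up data of extended subjects are discarded, or that on-drug concentrations are averaged into the washout PK row. The SAP supports neither reading.

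- The loss is confined to by-visit summaries. ADA categories use all available samples (4.2.9.3). Laboratory minimum, maximum and last values ignore windowing (3.3.4). Laboratory and vital-sign shift tables use all on-study data and ECG shift tables the last on-study observation (4.2.8.2 to 4.2.8.4). Adverse events go by onset date (3.3.2). The primary biopsy endpoint is an EOT value and is not windowed.
- The day rule in Section 4.2.9.1 excludes dosing-visit samples from the PK follow-up row.
- Mislabelling of other variables needs at least two extra doses and data actually collected at weeks 32, 36 or 40. The schedule of activities is in the protocol, which was not available for this check.
- Any assessment 4 or 8 weeks after EOT would remain in the window for one extra dose (days 253 and 281), and one of them for two extra doses (day 281).
- Section 1.2 lets a phone or virtual contact replace the last visit, so some final samples may not exist.

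It can also be said that the intent is clear: the follow-up rows carry the footnote's asterisk, and the footnote puts follow-up 12 weeks after EOT. That states when the visit happens but supplies no window, and the plan bars use of the visit label.

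All these limits stand. None of them gives the final follow-up visit of an extended subject a window.

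**Conclusion.** The point holds as a defect in the by-visit follow-up summaries. At nominal 4-weekly timing, the final follow-up visit after one to six extra doses is 15 to 155 days past the window and is missing from by-visit laboratory, vital-sign, ADA and PK tables. For PK, two stated conditions exclude each other. Data collected at extra-dose visits in weeks 32 to 40, if any, would be shown as follow-up for variables other than PK.

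The result rests on nominal timing and a last regular dose at week 24. With one extra dose, the final visit would have to be at least 15 days early to be captured, and a PK sample could qualify only if the last dose was before day 197.

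The SAP does not state how many subjects were extended. Purely as an assumption, 10% to 30% of the 55 planned tezepelumab subjects would be 55 × 0.10 = 5.5 to 55 × 0.30 = 16.5 final PK samples, an upper bound given the remote-visit option. Severity is moderate: no hypothesis test, primary estimate or cumulative safety result changes.

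**What to change.** Amend the Table 1 footnote before database lock, for subjects with extra doses only:

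- Anchor the follow-up window to the EOT visit, for example EOT+14 to EOT+97 days with target EOT+84. With no extra dose this returns 197 + 14 = 211 and 197 + 97 = 294. For one to six extra doses it gives 239-322, 267-350, 295-378, 323-406, 351-434 and 379-462. Each contains its own final visit day and starts 42 days after the last dose, so no dosing or EOT visit falls inside.
- State that an assessment on or before the EOT visit cannot be assigned to a follow-up window.
- Use the same anchor for PK and ADA follow-up. The PK-eligible days then overlap the window by 28 days, as they do now without extra doses.
- Leave unchanged the Section 3.1.6 rule that places early off-treatment follow-up assessments in planned-treatment windows. Re-anchoring all subjects would cut across it: a last dose at day 57 puts follow-up at 57 + 112 = day 169, now classed as Week 24.

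The cost is a revised footnote and windowing code. No new data are needed.
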